3.3.1.2.5 Duration

Duration is derived from the start and stop dates of the unsolicited AE:

- Duration = stop date of unsolicited AE - start date of unsolicited AE + 1.

The duration should be considered as missing only if one or both of the start and stop dates of the unsolicited AE is missing or partially missing.

3.3.1.2.6 Serious Adverse Events

An unsolicited event will be considered as a SAE if “Yes” is checked for “Serious” in the CRF.

3.3.1.2.7 Adverse Events of Special Interest

An unsolicited event will be considered as an AESI if “Yes” is checked for “Is the event an AESI?” in the CRF.

3.3.1.3 Other Safety Endpoints

3.3.1.3.1 Pregnancy

This information will not be included in the analysis but will be listed separately. No derivation or imputation will be done.

3.3.1.3.2 Action Taken

This information will be summarized as collected, including missing observations. No derivation or imputation will be done.

3.3.1.3.3 Seriousness

This information will be summarized as collected. No derivation or imputation will be done.

3.3.1.3.4 Outcome

This information will be summarized as collected. No derivation or imputation will be done.

3.3.1.3.5 Causal Relationship

This information will be summarized as collected in the field “Relationship to investigational product”. Missing causal relationship to study vaccine (investigational product) will be handled as described in [Section 4.3.2.2](#).

Relationship to study procedures for SAE is only presented in the listing.

3.3.1.3.6 Adverse Events Leading to Study Discontinuation

Adverse Events Leading to Study Discontinuation are defined as AEs leading to discontinuation of the study during active phase (from Visit 1 up to Visit 7). AEs leading to discontinuation of the study during safety follow-up phase (between Visit 7 and Phone call at Month 7) are not to be considered for this category. This information will be summarized as collected. A flag is available in the clinical database for all AEs in order to identify AEs leading to study discontinuation before the end of active phase.

In general, the items that are counted are:

- Disposition table: A subject who, on the “Completion at End of Study” form question “What was the participant’s status?” has “Adverse Event” checked.
- Safety overview table: A subject who has either on the “Completion at End of Study” form, question “What was the participant’s status?” has “Adverse Event” checked or lists a solicited AE that has “Caused Study Termination” checked that is at least Grade 1 or an unsolicited AE that has “Caused Study Discontinuation” checked that is at least Grade 1 or missing and is within the time period indicated.
- System Organ Class (SOC)/Preferred Term (PT) table: A solicited AE that has “Caused Study Termination” checked that is at least Grade 1 or an unsolicited AE that has “Caused Study Discontinuation” checked that is at least Grade 1 or missing and is within the time period indicated.

3.3.2 Immunogenicity

3.3.2.1 Computed Values for Analysis

In order to appropriately manage duplicate values for analysis purposes, the individual geometric mean (GM) of both values will be computed for each blood sample.

If a reported value is < Lower Limit of Quantitation (LLOQ) (ie, 0.2 IU/mL), then the computed value LLOQ/2 (ie, 0.1 IU/mL) will be used for the GM calculation.

For the qualitative Advisory Committee on Immunization Practices (ACIP) criteria reading (stated as Complete or Incomplete twice for each sample), the individual ACIP status will be derived as follows:

- If the 2 values are Complete, then the sample status will be Complete
- If the 2 values are Incomplete, then the sample status will be Incomplete
- If 1 value is Complete and the other one is Incomplete, the status will be Undefined
- If 1 value is Complete and other one is Not Reported, the status will be Complete
- If 1 value is Incomplete and other one is Not Reported, the status will be Incomplete
- If 2 values are Not Reported, the status will be Not Reported

There will be no Upper Limit of Quantitation (ULOQ) for the Rapid Fluorescent Focus Inhibition test (RFFIT) assay.

3.3.3 Efficacy

Not applicable.

3.3.4 Derived Other Variables

3.3.4.1 Duration of a Subject in the Study

The duration of a subject in the whole study (from Visit 1 up to end of 6-month follow up) is computed as: Maximum (Visit dates, Active phase termination date, Follow-up date) – Visit 01 date +1.

3.3.4.2 Duration of the Study

The duration of the active phase (from Visit 1 up to Visit 7) is computed as follows: Maximum of all subjects (Visit dates, Active phase termination date) - Minimum of all subjects (Visit 01 date) +1.

The duration of the follow-up is computed as: Maximum of all subjects (Follow-up date) - Minimum of all subjects (Follow-up date) + 1

The duration of the whole study (from Visit 1 up to end of 6-month follow up) is computed as: Maximum of all subjects (Visit dates, Active phase termination date, Follow-up date) – Minimum of all subjects (date of V01) +1.

3.3.4.3 Age and Age group

Age group is classified based on the age in years collected in eCRF, and the following age group will be derived in subgroup analysis: ≥ 18 to 40 years, ≥ 41 to 64 years, and ≥ 65 years.

The quantitative descriptive statistics (eg, Mean, SD, Max, Min, Median, Q1 and Q3) of age in demographics summary table(s) is based on the age in year collected in eCRF as well.

3.3.4.4 Vaccination Dose

For the same type of vaccine, if one vaccination was divided into several injections at one visit, all injections given at different sites within the same visit were considered as a single dose

4 Statistical Methods and Determination of Sample Size

The statistical analysis will be performed under the responsibility of the Sponsor's Biostatistics platform with the SAS software, at least version 9.4 (SAS Institute, Cary, North Carolina, USA).

The statistical analysis will be performed in 2 steps. A first statistical analysis will be carried out once all the safety and immunogenicity data collected up to D56, ie, up to 28 days after the last vaccine injection, will be obtained and locked. Then an addendum will be performed after the 6-month safety follow-up.

The results of the statistical analysis will be available in the final clinical study report (CSR).

For descriptive purposes, the following statistics will be presented:

Table 4.1: Descriptive statistics produced

Baseline characteristics and follow-up description	Categorical data	Number of subjects. Percentage of subjects.
	Continuous data	Mean, standard deviation, median, quartiles, minimum, and maximum.
Clinical safety results	Categorical data	Solicited: Number and percentage (95% confidence interval [CI] of subjects. Unsolicited: Number and percentage (95% CI) of subjects, and number of events.
Immunogenicity results	Categorical data (cutoff)	Number and percentage (95% CI) of subjects.
	Continuous data (titer / data)	Log10: Mean and standard deviation. Anti-Log10 (work on Log10 distribution, and anti-Log10 applied): Geometric mean, 95% CI of the geometric mean, median, quartiles, minimum, and maximum. Graphical representation by Reverse Cumulative Distribution Curve (RCDC).

The CI for the single proportion will be calculated using the exact binomial method (Clopper-Pearson method, quoted by Newcombe (1), ie, using the inverse of the beta integral with SAS®).

For immunogenicity results, assuming that Log10 transformation of the titers / data follows a normal distribution, at first, the mean and the 95% CI will be calculated on Log₁₀ (titers / data) using the usual calculation for normal distribution (using Student's t distribution with n-1 degree of freedom), then antilog transformations will be applied to the results of calculations, in order to provide GMs and their 95% CI.

GM is defined as follows:

$$GM = \left(\prod_{i=1}^n y_i \right)^{1/n} = 10^{\left(\frac{1}{n} \sum_{i=1}^n \log_{10}(y_i) \right)},$$

where (y₁,y₂,...,y_n) are the observed titers or individual ratios for each subject.

4.1 Statistical Methods

4.1.1 Hypotheses and Statistical Methods for Primary Objective

4.1.1.1 Hypotheses

The immunogenicity of VRVg-2 + HRIG will be compared to that of both Verorab + HRIG and Imovax Rabies vaccine + HRIG at D28, i.e., 14 days after the fourth vaccine injection, using a non-inferiority testing.

For each comparison, the primary parameter will be the difference of the proportion of subjects with an RVNA titer ≥ 0.5 IU/mL at D28 between the 2 compared vaccine groups. The hypotheses tested will be the following:

$$H_0: P_{VRVg-2+HRIG} - P_{control} \leq -5\%$$

$$H_1: P_{VRVg-2+HRIG} - P_{control} > -5\%$$

With P = proportion of subjects with an RVNA titer ≥ 0.5 IU/mL at D28 (%).

VRVg-2 will be considered as non-inferior to the tested control if the hypothesis H_0 is rejected.

4.1.1.2 Statistical Methods

For the non-inferiority hypothesis testing, the statistical methodology will be based on the use of the two-sided 95% CI of the difference of proportions of subjects with an RVNA titer ≥ 0.5 IU/mL at D28 between the VRVg-2 vaccine + HRIG group (Group 1) and the comparator vaccine groups (Group 2 and Group 3). The 95% CI for differences will be calculated using Wilson score method without continuity correction (2).

Let $\hat{\theta} = p_1 - p_2$, then $L = \hat{\theta} - \delta$ and $U = \hat{\theta} + \varepsilon$ are respectively the lower and the upper limits of the CI, where:

$$\delta = Z_{0.025} \sqrt{\left\{ \frac{l_1(1-l_1)}{n_1} + \frac{u_2(1-u_2)}{n_2} \right\}}$$

$$\varepsilon = Z_{0.025} \sqrt{\left\{ \frac{l_2(1-l_2)}{n_2} + \frac{u_1(1-u_1)}{n_1} \right\}}$$

l_1 and u_1 are calculated from the CI of the single proportion in Group 1 given by:

$$\frac{(2n_1p_1 + Z_{0.025}^2 \pm Z_{0.025} \sqrt{(Z_{0.025}^2 + 4n_1p_1(1-p_1))})}{2(n_1 + Z_{0.025}^2)}$$

l_2 and u_2 are calculated from the CI of the single proportion in comparator vaccine group (Group 2 or Group 3) given by:

$$\frac{(2n_2 p_2 + Z_{0.025}^2 \pm Z_{0.025} \sqrt{(Z_{0.025}^2 + 4n_2 p_2(1-p_2))}}{2(n_2 + Z_{0.025}^2)}$$

where $Z_{0.025}$ is the upper 97.5th percentile of the standard normal distribution.

Each non-inferiority will be demonstrated if the lower limit of the 95% CI of the difference of the 2 proportions $P_{VRVg-2} - P_{control}$ is $> -5\%$ at D28.

Overall non-inferiority will be demonstrated if both of the non-inferiority between VRVg-2 + HRIG and Verorab vaccine + HRIG and between VRVg-2+HRIG and Imovax Rabies vaccine + HRIG are demonstrated at D28.

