Planned Sample Size:	
Originally, it was planned to enroll 504 subjects in this study. Following a clinical hold between Friday, 06 September 2019 and Tuesday, 10 September 2019, for the evaluation of a serious adverse event (SAE) as required by the Agence Nationale de Sécurité du Médicament et des Produits de Santé (ANSM), the sample size of the study had been modified to replace subjects who were to be excluded from the per protocol analysis set (PPAS) due to vaccination outside of the recommended time window and to increase the attrition rate of the study. Consequently 606 subjects were planned to be enrolled.
 
As a consequence of the COVID-19 pandemic lockdown established by the French government, the study was put on hold. Enrollment was paused from the 12th of March 2020 and vaccinations were stopped on the 16th March 2020 for twenty-nine subjects who are expected to be withdrawn and excluded from the PPAS as they will be unable to complete their vaccination schedule as planned in the protocol. The sample size of the study will then be modified to replace these subjects.
 
Now, a minimum of 636 subjects are planned to be enrolled: 318 in the VRVg-2 + HRIG group, and 106 in each of the remaining groups (Verorab vaccine + HRIG, Imovax Rabies vaccine + HRIG, and VRVg-2). One hundred subjects who will be excluded from the PPAS (71 from the first hold, 29 in the COVID-19 context) will be replaced and 1 additional subject will be added to keep the randomization ratio. A maximum dropout rate of 20% is anticipated.
 
In case of any new study hold, withdrawn or out of vaccination time windows subjects might be replaced and sample size might be increased accordingly.

Duration of Participation in the Study:	The duration of each subject's participation in the trial will be approximately 7 months (28 day-vaccination period followed by 6-month safety follow-up period).
Investigational Product:	The investigational product is VRVg: Purified Vero Rabies Vaccine – Serum Free (purified inactivated rabies vaccine prepared on Vero cell line)
Form:	Freeze-dried
Composition:	Each 0.5 mL dose contains:

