Statistical Methods:	
The statistical analysis will be performed in 2 steps. A first statistical analysis will be done once all safety and immunogenicity data collected up to D56, ie, up to 28 days after the last vaccine injection, will be obtained and locked. Then an addendum will be done after the 6-month safety follow-up.
 
The immunogenicity of VRVg-2 + HRIG will be compared to that of Verorab vaccine + HRIG and Imovax Rabies vaccine + HRIG at D28, ie, 14 days after the fourth vaccine injection, using a non-inferiority testing.
 
For each comparison, the primary parameter will be the difference of the proportions of subjects with an RVNA titer ≥ 0.5 IU/mL at D28 between the 2 compared vaccine groups. The hypotheses tested will be the following:
 
$H_0: P_{VRVg-2} - P_{control} \leq -5\%$
 
$H_1: P_{VRVg-2} - P_{control} > -5\%$
 
With P=proportion of subjects with an RVNA titer ≥ 0.5 IU/mL at D28 (%).
 
VRVg-2 will be considered as non-inferior to the tested control if the hypothesis H_0 is rejected.
 
For the non-inferiority hypotheses, the statistical methodology will be based on the use of the two-sided 95% confidence interval (CI) of the difference of proportions of subjects with an RVNA titer ≥ 0.5 IU/mL at D28. The 95% CI for differences will be calculated using Wilson score method without continuity correction.
 
Each non-inferiority will be demonstrated if the lower limit of the 95% CI of the difference of the 2 proportions $P_{VRVg-2} - P_{control}$ is $> -5\%$.
 
Overall, non-inferiority will be demonstrated if each of the non-inferiority between VRVg-2 + HRIG and both Verorab vaccine + HRIG and Imovax Rabies vaccine + HRIG is demonstrated.
 
Both the PPAS (as the main analysis for non-inferiority) and the Full Analysis Set for Immunogenicity (FASI) excluding subjects with a D0 titer missing or a titer ≥ 0.5 IU/mL will be used in the primary analysis.
 
If the primary objective is reached, the following hypotheses will be tested at D28, as part of the secondary objectives:

^a Chronic illness may include, but is not limited to, neurological, cardiopulmonary, gastrointestinal, renal, genitourinary, metabolic, hematologic, auto-immune, or psychiatric disorders or infection.

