5.1.2 Justification of the Study Design

VRV13 will use the simulated post-exposure ESSEN regimen, ie, in 5 injections, on D0, D3, D7, D14, and D28. In detail, the performance of VRVg-2 (+ HRIG) will be demonstrated through the non-inferiority to both Verorab vaccine (+ HRIG) and Imovax Rabies vaccine (+ HRIG), in terms

of proportion of subjects achieving an RVNA titer ≥ 0.5 IU/mL^a at D28 (ie, 14 days after the fourth vaccine injection [primary objective]), with an expected endpoint of at least 95% seroconversion rate at this time point (secondary objective).

The design and endpoints were agreed with the EMA^b and the US FDA^c.

A VRVg-2 group without HRIG administration will be added to allow for the description of differences in the immunological response between VRVg-2 with, and without HRIG administration.

Overall the design of this study will be consistent with previous VRVg trials and WHO guidelines, and will also be in line with latest recommendations from the WHO (April 2018; ie, PEP regimen consisting of 4 IM doses D0, D3, D7 and between D14 and D28) (21), and current ACIP guidance (dated 2010; ie, 4 IM dose schedule on D0, D3, D7, and D14) (22), since timely assessment after the fourth vaccine injection at D28 is planned.

Other noteworthy design features of this study are:

- Verorab and Imovax Rabies vaccines are both current standard of care employed globally. Their inclusion as controls/comparators aims supporting VRVg licensure worldwide. However, demonstration of non-inferiority to Verorab is not required for study success to support licensure in the US.
- The choice of France as the country for conducting the study was driven by the local regulatory context and the feasibility for using both Verorab and Imovax Rabies as vaccine comparators in rabies-naïve population.
- The choice to include adults aged ≥ 18 years without upper age limit aims at supporting a vaccine indication covering all age groups. It is to note that the results obtained in VRV13 will be extrapolated to the pediatric population since the risk-benefit of the administration of HRIG in simulated conditions in this population is not justified.
- Randomization of participants will be by IRT (stratified by center), in 3:1:1:1 ratio (Group 1 to Group 4), respectively.

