12.1.1.2 Statistical Methods

For the non-inferiority hypothesis testing, the statistical methodology will be based on the use of the two-sided 95% CI of the difference of proportions of subjects with an RVNA titer ≥ 0.5 IU/mL at D28 between the VRVg-2 vaccine group and the comparator. The 95% CI for differences will be calculated using Wilson score method without continuity correction (31).

Each non-inferiority will be demonstrated if the lower limit of the 95% CI of the difference of the 2 proportions $P_{VRVg-2} - P_{control}$ is $> -5\%$.

Overall non-inferiority will be reached if each of the non-inferiority between VRVg-2 + HRIG and both Verorab vaccine + HRIG and Imovax Rabies vaccine + HRIG will be demonstrated.

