12.5 Determination of Sample Size and Power Calculation

The sample size calculation is driven by the non-inferiority testing.

An alpha level of 2.5% (one-sided hypothesis), a maximum acceptable difference of 5% for the proportion of subjects with an RVNA titer ≥ 0.5 IU/mL at D28, and a power of at least 90% for each of the non-inferiority testing have been chosen to calculate the sample size, in order to ensure an overall power of at least 80% to reach the primary objective. Assuming a proportion of subjects with an RVNA titer ≥ 0.5 IU/mL of 99% for the 3 vaccine groups, and an unbalanced randomization 3:1:1 (VRVg-2 + HRIG : Verorab vaccine + HRIG : Imovax Rabies vaccine + HRIG), 213 subjects in the VRVg-2 + HRIG group and 71 subjects in each of the Verorab vaccine + HRIG and Imovax Rabies vaccine + HRIG groups will be necessary, to provide a power of 80% to test the global null hypothesis, using the Farrington and Manning method (34).

Originally, it was planned to enroll 504 subjects in this study. Following a clinical hold between Friday, 06 September 2019 and Tuesday, 10 September 2019, for the evaluation of an SAE as required by the ANSM, the sample size of the study had been modified to replace subjects who were to be excluded from the PPAS due to vaccination outside of the recommended time window and to increase the attrition rate of the study.

Under the assumption that 20% of subjects will not be evaluable, 267 subjects in the VRVg-2 + HRIG group and 89 subjects in each, the Verorab vaccine + HRIG and the Imovax Rabies vaccine + HRIG groups should be enrolled.

As a consequence of the first clinical hold of the study, 71 subjects from the 4 vaccine groups (assumed to be distributed with a distribution close to 36:12:12:12) were identified as to be excluded from the PPAS. With the aim to secure the study power, 60 additional subjects were to be enrolled among the 3 vaccine groups involved in the primary objective assessment, ie, a total

of 606 subjects were to be enrolled as follows: 303 in the VRVg-2 + HRIG group and 101 in each of the Verorab vaccine + HRIG and Imovax Rabies vaccine + HRIG groups.

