Then, in the context of the COVID-19 crisis, enrollment was paused from the 12th of March 2020 and ongoing vaccination were stopped on the 16th of March 2020. Twenty-nine ongoing subjects (from all the 4 groups) are expected to be withdrawn and excluded from the PPAS as they are unable to complete their vaccination schedule as planned in the protocol due to national confinement measures. Still with the aim to secure the study power and maintain the randomization ratio, 30 additional subjects will be enrolled in the study. Finally, 636 subjects are planned to be enrolled, with a planned overall distribution of 318:106:106:106 among the 4 vaccine groups. Assuming a proportion of subjects with an RVNA titer ≥ 0.5 IU/mL of 99% in the VRVg-2 + HRIG group, this sample size will give more than 93% of power to demonstrate the superiority of this rate to 95% on the PPAS. In order to maintain the 3:1:1:1 ratio, the additional arm of subjects receiving VRVg-2 as standalone will include 106 subjects; the results will be descriptive, mainly versus the VRVg-2 + HRIG group. The number of subjects is the same as the 2 controls to facilitate group allocation and will allow good precision of the results.

The 3:1:1 design is chosen to optimize the non-inferiority testing for immunogenicity with 2 comparators and to increase the size of the safety database of VRVg-2 vaccine.

In case of any new study hold, withdrawn or out of vaccination time windows subjects might be replaced and sample size might be increased accordingly.

13 Ethical and Legal Issues and Investigator / Sponsor Responsibilities

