4.5 Determination of Sample Size and Power Calculation

The sample size calculation is driven by the non-inferiority testing.

An alpha level of 2.5% (one-sided hypothesis), a maximum acceptable difference of 5% for the proportion of subjects with an RVNA titer ≥ 0.5 IU/mL at D28, and a power of at least 90% for each of the non-inferiority testing have been chosen to calculate the sample size, in order to ensure an overall power of at least 80% to reach the primary objective. Assuming a proportion of subjects with an RVNA titer ≥ 0.5 IU/mL of 99% for the 3 vaccine groups, and an unbalanced randomization 3:1:1 (VRVg-2 + HRIG: Verorab vaccine + HRIG: Imovax Rabies vaccine + HRIG), 213 subjects in the VRVg-2 + HRIG group and 71 subjects in each of the Verorab vaccine + HRIG and Imovax Rabies vaccine + HRIG groups will be necessary, to provide a power of 80% to test the global null hypothesis, using the Farrington and Manning method (4).

Originally, it was planned to enroll 504 subjects in this study. Following a clinical hold between Friday, 06 September 2019 and Tuesday, 10 September 2019, for the evaluation of an SAE as required by the ANSM, the sample size of the study had been modified to replace subjects who were to be excluded from the PPAS due to vaccination outside of the recommended time window and to increase the attrition rate of the study.

Under the assumption that 20% of subjects will not be evaluable, 267 subjects in the VRVg-2 + HRIG group and 89 subjects in each, the Verorab vaccine + HRIG and the Imovax Rabies vaccine + HRIG groups should be enrolled.

As a consequence of the first clinical hold of the study, 71 subjects from the 4 vaccine groups (assumed to be distributed with a distribution close to 36:12:12:12) were identified as to be excluded from the PPAS. With the aim to secure the study power, 60 additional subjects were to be enrolled among the 3 vaccine groups involved in the primary objective assessment, ie, a total of 606 subjects were to be enrolled as follows: 303 in the VRVg-2 + HRIG group and 101 in each of the Verorab vaccine + HRIG and Imovax Rabies vaccine + HRIG groups.

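### Does deciding non-inferiority by the Newcombe-Wilson interval, whose exact error is 3.10% at 213:71, break the planned one-sided 2.5% alpha?

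*SAP*

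**What the plan says.** SAP 4.5 and Protocol 12.5 set the design inputs: "An alpha level of 2.5% (one-sided hypothesis), a maximum acceptable difference of 5" percentage points, and at least 90% power for each non-inferiority test. With 99% responders assumed in all three HRIG groups, 213 and 71 evaluable subjects are said "to provide a power of 80% to test the global null hypothesis, using the Farrington and Manning method".

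The deciding rule is a different one. Protocol 12.1.1.2 reads "The 95% CI for differences will be calculated using Wilson score method without continuity correction (31", and SAP 4.1.1.2 repeats it ("The 95% CI for differences will be calculated using Wilson score method without continuity correction (2") and prints the formula. A comparison succeeds if the lower limit of the two-sided 95% interval is above -5%. Overall success needs both comparisons.

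The Protocol synopsis makes the per-protocol set (PPAS) the main analysis set: "Both the PPAS (as the main analysis for non-inferiority) and the Full Analysis Set for Immunogenicity (FASI". Its final size is not fixed. It depends on the two holds, on the replacements ("30 additional subjects will be enrolled in the study") and on attrition ("A maximum dropout rate of 20% is anticipated"). Neither document gives the actual error of the interval rule or describes 2.5% as nominal.

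**The concern.** The stated alpha belongs to the sizing calculation, while the trial is decided by another procedure. With response rates near 100% and only 71 to 89 subjects in each control group, the interval is discrete and its true error can differ from 2.5%. If that error is higher, a vaccine that is truly 5 points worse passes slightly more often than the plan suggests.

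The joint requirement softens this, but Protocol 5.1.2 says that "demonstration of non-inferiority to Verorab is not required for study success to support licensure in the US". A reader interested in the United States may therefore look at the Imovax comparison alone, where the joint protection is absent and 2.5% would be taken at face value.

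**Working it through.** **1. The plan's own figure.** Inputs from SAP 4.5: 99% in both groups, margin 5 points, ratio 3:1, one-sided 2.5%. Under the null constraint the restricted estimates are 0.9472 and 0.9972.

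- Null SE: √(0.9472×0.0528/213 + 0.9972×0.0028/71) = 0.01656
- SE at 99%: √(0.99×0.01×(1/213 + 1/71)) = 0.01364
- Power: Φ((0.05 - 1.96×0.01656)/0.01364) = Φ(1.29) = 90.1%

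At 210:70 the power is 89.6%, so 71 is the smallest control group that reaches 90%. Dividing by 0.8 and rounding up gives 267 and 89. The plan's sizes reproduce.

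**2. Exact error of the deciding rule.** For each pair of counts, SAP 4.1.1.2 gives L = p1 - p2 - 1.96√(l1(1-l1)/n1 + u2(1-u2)/n2), where l1 and u2 are Wilson limits. The error is the sum of the two binomial probabilities over all pairs with L > -0.05, with VRVg-2 set 5 points below control. Farrington-Manning is enumerated in the same way (pass if z ≥ 1.96). At 213:71:

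| Control rate | Newcombe-Wilson | Farrington-Manning |
|---|---|---|
| 95% | 3.20% | 3.19% |
| 96% | 3.18% | 3.14% |
| 97% | 3.13% | 2.97% |
| 98% | 3.17% | 2.71% |
| 99% | 3.10% | 2.50% |
| 99.5% | 2.67% | 2.36% |
| 100% | 1.70% | 1.70% |

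Only 99% is a plan assumption; the other rates are sensitivity values.

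**3. What separates the methods at 213:71.** Only one plausible table does: 8/213 failures against 2/71. There p1 - p2 = 0.9624 - 0.9718 = -0.0094, l1 = 0.9277 and u2 = 0.9922. So L = -0.0094 - 1.96√(0.9277×0.0723/213 + 0.9922×0.0078/71) = -0.0497, which passes, while the Farrington-Manning statistic falls short of 1.96. The table has probability 0.59% at 94% against 99%, which is the whole gap between 3.10% and 2.50% (before rounding). At 99% in both groups its probability is 0.015%. The other three discordant tables have 35 or more VRVg-2 failures.

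**4. Plausible PPAS sizes.** The first hold removes about 36:12. The second is taken as 15:5, an assumption matched to the 30 replacements. Then 318-36-15 = 267 and 106-12-5 = 89, and 80% of these is about 213 and 71. Over the 19 exact 3:1 sizes between those ends, the Newcombe-Wilson error is:

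| Control rate | Range | Mean | Sizes above 2.5% |
|---|---|---|---|
| 99% | 2.46-3.13% | 2.80% | 16 of 19 |
| 99.5% | 1.87-2.97% | 2.44% | 9 of 19 |
| 100% | 1.01-2.47% | 1.68% | 0 of 19 |

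At 99%, Farrington-Manning gives 2.29-2.72%, mean 2.49%, and is above 2.5% at 8 of 19 sizes. At 95-98% both methods exceed 2.5% at all 19 sizes. The highest values over 95-99% are 3.66% (Newcombe-Wilson, 228:76, control 95.6%) and 3.33% (Farrington-Manning, 234:78, control 95.5%).

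The gap depends on both size and rate. At 255:85 it is nil at 99% (2.48% both), but at 95% the figures are 3.41% and 2.96%.

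**5. The decision actually taken.** At 213:71, with VRVg-2 at 94% and both controls at 99%, false overall success is 1.15%. It is 2.90% if one control is itself at 94%. Over the 19 sizes with both controls at 99% it is 0.74-1.31%.

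**6. Power.** At 213:71 and 99% in both groups, exact power per comparison is 96.64% (Newcombe-Wilson) and 96.63% (Farrington-Manning).

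**The case for a change.** The best case for acting has three parts. The excess is real at the rate the plan assumes, at 16 of 19 plausible sizes. The final PPAS counts are open, so a reader cannot infer the error from the stated 2.5%. And where the Imovax comparison is read alone, the relevant figure is the per-comparison error, which reaches 3.66% if a control rate as low as 95.6% is allowed. Disclosure costs little.

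The first two parts stand as facts: 2.5% is nominal, and the exact level can only be tabulated once the counts are known. They do not show a defect. The excess shrinks and then disappears above 99%, and Protocol 1.2 describes the expected level in earlier trials as more than 99%. That evidence is imperfect, because the three trials concerned are not described as giving HRIG. The 3.66% rests on a control rate the plan does not assume.

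The United States argument is thin. Protocol 5.1.2 defines no separate Imovax test or alpha. The table that separates the methods at 213:71 would also fail the secondary 95% objective, since the exact lower limit for 205/213 is 92.7%.

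**Conclusion.** No change to the plan. The 3.10% is correct for 213:71 at 94% against 99%, but it is the ordinary behaviour of an approximate interval on discrete data. There is no wrong formula, contradiction or undefined step. At the assumed 99% the excess over 2.5% is at most 0.63 points (3.13 - 2.50) across the 19 sizes, and the joint rule keeps false success at 0.74-1.31% with both controls at 99%.

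The alternatives bring no clear gain. Farrington-Manning also exceeds 2.5% at many sizes and rates and leaves power unchanged. An exact test would hold the level but would give up some power. Replacing a pre-specified primary interval now would also be hard to defend, because the SAP version history places version 1.1 after unblinding of the active phase.

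If the authors wish, the report can call 2.5% nominal and tabulate the exact per-comparison and joint error at the realised PPAS counts over control rates of 95-100%. That is optional reporting.

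The conclusion rests on PPAS counts near 3:1 between 213:71 and 267:89, on the assumed 15:5 split of the second hold, and on control rates of 95-100%, of which only 99% is the plan's.
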